11. SAFETY ANALYSIS

The purpose of this section is to define the safety parameters for the study. All summaries of safety data will be conducted using the safety population.

Besides the safety analysis described in this section, additional safety analysis may be performed, displayed and summarized, when deemed necessary.

11.1. Adverse Events

Adverse events (AEs) will be coded according to the MedDRA version 21.0 or higher. The severity of AEs will be assessed by the investigator according to the Common Terminology Criteria for Adverse Events (CTCAE) version 4.0. For any AE not listed in the CTCAE grading system, the severity of these events will be assessed by the Investigator using a 5-point scale as described in Section 11.2.2. of the protocol.

Treatment-emergent adverse events (TEAEs) are defined as any AE occurring or worsening with an onset date on or after the date of the first dose of the study medication and within 28 days after the date of the last dose. AEs will be summarized by SOC, preferred term (PT) and treatment group. The AE summaries will include incidence tables of:

- Summary of TEAEs.
- TEAEs.
- Treatment-related TEAEs.
- Serious TEAEs.
- Treatment-related serious TEAEs.
- TEAEs with CTCAE toxicity grade of 3 or 4.
- Treatment-related TEAEs with CTCAE toxicity grade of 3 or 4.
- Serious TEAEs with severity of grade 3 or 4.
- Treatment-related Serious TEAEs with severity of grade 3 or 4.
- TEAE leading to death.
- TEAEs leading to dose reduction.
- TEAEs leading to dose interruption.
- TEAEs leading to dose interruption and reduction.
- TEAEs leading to treatment discontinuation.
- Treatment-related TEAEs leading to death.
- TEAEs by maximum severity.
- TEAEs by age group (<65, 65 to 74, ≥75 years).
- TEAEs by sex.
- TEAEs by decreasing order of frequency of preferred term.

- TEAEs by decreasing order of frequency of system organ class.
- Serious TEAEs by decreasing order of frequency of preferred term.
- Serious TEAEs by decreasing order of frequency of system organ class
- Pre-treatment AEs.
- Non-serious TEAEs

Subjects with multiple events reported for the same preferred term will be counted only once per SOC and PT level. For summaries by severity (CTCAE grade), if a subject experience the same PT multiple events, then the subject will be counted only once and for the greatest severity.

In summaries of treatment-related TEAEs, if a subject reports multiple occurrences of the same AE, only the treatment-related occurrence will be summarized. Adverse events with missing relationship to study medication will be imputed as related to study medication.

Additionally, the exposure-adjusted incidence rate (EAIR) per 100 person-years will be summarized for all TEAEs and Grade 3 or 4 TEAEs by system organ class, preferred term, and treatment group. The EAIR per 100 person-years is defined as $100 \cdot (n/T)$, where n is the number of subjects with the specific AE at the SOC or PT level, and T is total exposure time (in years) among subjects included in the analysis. Subjects with multiple occurrences of the specific event will be counted only once in the numerator. The exposure time for a subject without the specific event is the treatment duration (calculated as $\text{Min}[\text{death date, last dose date} + 28] - \text{first dose date} + 1$ day), whereas the exposure time for a subject with the specific event is the treatment duration up to the start date (inclusive) of the first occurrence of the specific event. The total exposure time in years is calculated by dividing the sum of exposure time in days over all subjects included in the analysis by 365.25. The EAIR per 100 person-years is interpreted as the expected number of subjects with at least one occurrence of the specific event per 100 person-years of exposure to the study drug.

Listings for the corresponding summary tables for TEAE, Serious TEAE, TEAEs leading to study drug discontinuation and TEAEs leading to death will be presented separately.

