1.4.1 Risk Assessment

Potential Risk of Clinical Significance	Summary of Data/Rationale for Risk	Mitigation Strategy
Study Intervention - Azacitidine		
Neutropenia and severe infections	In subjects randomized to oral azacitidine 300 mg at 21-day treatment schedule, the most frequent hematological AEs were neutropenia, febrile neutropenia,	To mitigate risk of severe infections, during Cycles 1 and 2 (higher risk period for severe infections) the subjects will receive oral azacitidine for 14 days of a 28-day cycle

Potential Risk of Clinical Significance	Summary of Data/Rationale for Risk	Mitigation Strategy
	
and associated infections. There was an imbalance in incidence of death between the drug and placebo treatment groups. Most of the death cases in the oral azacitidine-treated subjects occurred during the first 56 days on treatment with infections being the leading cause of death. Affected subjects showed lower median ANC at baseline, which could have made them more susceptible for severe infections.
	
schedule. The treatment can be extended to a 21-day schedule after Cycle 2, if a subject did not experience Grade 3 or 4 toxicities requiring dose delay or reductions and if there is no evidence of hematological improvement on 14-day dosing schedule.
 
During the first 2 cycles on treatment subjects' blood counts will be monitored on weekly basis, reducing to biweekly monitoring up to Cycle 12.
 
Guidance for IP dose modification due to toxicities including neutropenia and febrile neutropenia is provided in Section 8.2.4 and Table 2 of the Protocol.
 
A strong recommendation regarding administration of prophylactic fluoroquinolone antibiotics or other recognized prophylactic antibiotics was provided for subjects who develop Grade 4 neutropenia (see Section 9.1).

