10.1 Overview

This phase 3, multicenter, randomized, double-blind, placebo-controlled, parallel-group study is designed to compare the efficacy and safety of oral azacitidine plus best supportive care versus placebo plus best supportive care in subjects with RBC transfusion-dependent anemia and thrombocytopenia (platelet count $\leq 75 \times 10^9/L$) due to IPSS lower-risk MDS.

All data will be summarized by treatment group. In addition, where appropriate, a total column will be included to summarize subjects across treatment groups. Summaries of continuous variables will present the number of subjects included in the analysis (N), the mean and standard deviation (SDev) of the mean, the median, the minimum, and the maximum statistics. Counts and percentages will be presented in summaries of categorical variables. The denominator for each percentage will be the number of subjects in the population treatment group unless otherwise specified. In general, missing data will not be imputed unless otherwise specified.

All statistical analyses specified in this protocol will be conducted using SAS[®] Version 9.2 or higher unless otherwise specified.

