10.7 Safety Analysis

All safety analyses will be performed on the safety population.

Adverse events (AEs) will be coded using MedDRA. Adverse event listings will include the verbatim term and the MedDRA preferred term. Treatment-emergent AEs (TEAEs) will be summarized by worst severity grade, system organ class, and preferred term. Treatment-emergent AEs leading to death or to discontinuation from treatment, AEs classified as CTCAE (Version 4.0) Grade 3 or Grade 4, AEs related to IP and SAEs will be summarized separately. Listings of all deaths and all SAEs, regardless of when they occurred, will also be generated. Progression to AML and development of a second primary malignancy will be documented as an SAE (considered to be at least an AESI even if no other seriousness criteria apply) throughout a subject's duration in the study (from the time of signing ICD until death, lost to follow-up, or withdrawal of consent for further data collection). AESIs, based on appropriate Standardized MedDRA Queries (SMQs), will also be summarized.

Clinical laboratory results will be summarized descriptively by treatment group, which will also include a display of change from baseline. Laboratory values outside of the normal ranges will be identified. Clinically significant hematologic and non-hematologic laboratory abnormalities that meet Grade 3 or Grade 4 criteria according to the CTCAE will be listed and summarized. Graphical display of select laboratory parameters over the course of the study will be provided.

Vital sign measurements and ECOG performance status will be listed for each subject at each visit. Descriptive statistics for vital signs and ECOG performance status, both observed values and changes from baseline, will be summarized by treatment group.

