11.2.2 Severity / Intensity

The severity / intensity of AEs will be graded based upon the subject's symptoms according to the currently active minor version of Common Terminology Criteria for Adverse Events (CTCAE, Version 4.0);

http://ctep.cancer.gov/protocolDevelopment/electronic_applications.ctc.htm#ctc_40

AEs that are not defined in the CTCAE should be evaluated for severity according to the following scale:

- Grade 1 = Mild – transient or mild discomfort; no limitation in activity; no medical intervention/therapy required
- Grade 2 = Moderate – mild to moderate limitation in activity, some assistance may be needed; no or minimal medical intervention/therapy required
- Grade 3 = Severe – marked limitation in activity, some assistance usually required; medical intervention/therapy required, hospitalization is possible
- Grade 4 = Life threatening – extreme limitation in activity, significant assistance required; significant medical intervention/therapy required, hospitalization or hospice care probable
- Grade 5 = Death - the event results in death

The term “severe” is often used to describe the intensity of a specific event (as in mild, moderate or severe myocardial infarction); the event itself, however, may be of relatively minor medical significance (such as severe headache). This criterion is *not* the same as “serious” which is based on subject/event *outcome* or *action* criteria associated with events that pose a threat to a subject’s life or functioning.

Seriousness, not severity, serves as a guide for defining regulatory obligations.

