11.1.1. Adverse Events by Cycle

The following TEAEs will be summarized by incidence tables, for the safety population by treatment group and cycle group:

- All TEAEs
- Serious TEAEs
- TEAEs with severity of grade 3 or 4;
- TEAEs leading to death
- Treatment-related TEAE leading to death
- TEAEs leading to study medication discontinuation

The following cycle group will be used:

- Cycles 1-2

- Cycles 3-4
- Cycles 5-6
- Cycles 7-12
- Cycles 13-24
- Cycles > 24

The analysis of TEAE by cycle of onset for any occurrence will be based on the onset date of AE to determine the cycle. AEs with a duration that overlaps multiple cycles will only be counted in the first overlapped cycle. Subjects with multiple occurrences reported with the onset date within the same cycle for the same SOC / PT will be counted once per SOC level / PT level within the cycle.

TEAEs by cycle day of onset for any occurrence will also be summarized. The cycle day will be grouped as: cycle days 1-7, cycle days 8-14, cycle days 15-21, and cycle days >21.

The first occurrence of TEAEs by cycle of onset, and by cycle day of onset will be summarized by SOC and PT. Subjects with multiple occurrences reported for the same SOC / PT will be counted only once based on the earliest onset date (the first occurrence) per SOC level / PT level.

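### Grade-limited AE tables and the severe EAIR stop at Grade 4, and by-cycle percentages default to the whole treatment group as denominator

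*SAP*

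**What the plan says.** **Severity cut.** SAP 11.1 lists an incidence table of "TEAEs with CTCAE toxicity grade of 3 or 4" and adds that the "exposure-adjusted incidence rate (EAIR) per 100 person-years will be summarized for all TEAEs and Grade 3 or 4 TEAEs". The by-cycle list in SAP 11.1.1 has "TEAEs with severity of grade 3 or 4". SAP 11.1.2 applies the same cut to the adverse events of special interest (AESIs), of which infection is one category. Protocol 10.7 likewise calls for a summary of "AEs classified as CTCAE (Version 4.0) Grade 3 or Grade 4". The severity scale in Protocol 11.2.2 has a further step: "Grade 5 = Death - the event results in death".

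**EAIR.** SAP 11.1 defines the rate as 100 times the number of subjects with the event, divided by total exposure in years. A subject with the event contributes time to first onset. A subject without it contributes time to death or to 28 days after the last dose, whichever is earlier.

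**By-cycle denominators.** SAP 11.1.1 says: "The following TEAEs will be summarized by incidence tables, for the safety population by treatment group and cycle group". It mentions no number at risk. Protocol 10.1 sets the general rule: "The denominator for each percentage will be the number of subjects in the population treatment group unless otherwise specified". SAP 16 lists the departures from the protocol's statistical section, does not include this one, and states that there are no others.

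**The concern.** Protocol 1.4.1 reports an imbalance in deaths between the arms and says: "Most of the death cases in the oral azacitidine-treated subjects occurred during the first 56 days on treatment with infections being the leading cause". The most severe infections are thus part of the trial's named safety signal. A severe-infection row or rate that stops at Grade 4 leaves out any subject whose infection was recorded once, as fatal. The rate that a reader would naturally use to compare severe infection between arms, after allowing for exposure, is then incomplete at its worst end.

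The denominator issue affects the other axis, time on treatment. If subjects who stopped or died before Cycle 13 stay in the denominator for Cycles 13-24, the percentage mixes risk with retention. If retention differs by arm, the between-arm comparison in later cycles is affected as well.

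**Working it through.** The documents state no EAIR or by-cycle percentage, so there is no figure of that kind to reproduce. The survival assumptions used below come from SAP 4.4, and its power figure does reproduce: √205/2 × |ln 0.70| − 1.96 = 0.593, and Φ(0.593) = 72.4%, against the stated 72%.

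**Step 1: where a fatal-only infection is counted.**

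| Output | Fatal-only infection counted? |
|---|---|
| Grade 3 or 4 TEAE and AESI tables, overall and by cycle | No |
| Grade 3 or 4 EAIR | No; its time up to death is in the exposure total |
| All-TEAE tables and EAIR; AESI EAIR (no grade limit stated) | Yes, mixed with all grades |
| Serious TEAEs and AESIs, overall and by cycle | Yes, mixed with serious events of any grade |
| Leading-to-death tables, overall and by cycle | Yes, alone |
| TEAEs by maximum severity | Yes, overall only |

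No EAIR and no by-cycle table gives Grades 3 to 5 together. Adding the Grade 3 or 4 row to the fatal row does not supply it, because a subject with one non-fatal severe infection and a later fatal one may be in both. SAP 11.1 counts repeat events of one preferred term once, at the greatest severity. It does not say whether a Grade 3 event followed by a fatal one of the same term then leaves the Grade 3 or 4 row.

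**Step 2: size for the EAIR (assumed inputs).** Take 108 treated in an arm, 30 with a Grade 3 or 4 infection at mean onset 0.2 years, 5 with only a fatal record (onset day 28, death day 45), and 73 event-free with mean exposure 0.75 years.

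- Grade 3 or 4: exposure = 30×0.2 + 5×45/365.25 + 73×0.75 = 61.37 years; rate = 100×30/61.37 = 48.9.
- Grade 3 to 5: exposure = 30×0.2 + 5×28/365.25 + 73×0.75 = 61.13 years; rate = 100×35/61.13 = 57.3.

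The Grade 3 or 4 rate is 15% lower. With 20 to 40 Grade 3 or 4 subjects, 2 to 10 fatal-only subjects and 0.5 to 1.0 years of event-free exposure, the shortfall runs from about 5% to 34%. Nearly all of it comes from the numerator.

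**Step 3: direction (assumed counts, equal arms).** With 20 Grade 3 or 4 plus 10 fatal-only subjects on azacitidine, and 15 plus 3 on placebo, the risk ratio is 20/15 = 1.33 on Grade 3 or 4 and 30/18 = 1.67 on Grade 3 to 5. Exchange the fatal-only counts and it moves from 1.33 to 23/25 = 0.92. The cut can hide an excess or create one.

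**Step 4: by-cycle denominators.** Assume exponential survival with the planning medians of 18 months (placebo) and 25.7 months (azacitidine), undelayed 28-day cycles, and loss from death only. Cycle c starts at (c−1)×28/30.4375 months. The share remaining is S = 2^(−t/median), and the true percentage is 1/S times the tabulated one.

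| Start of | t (months) | Placebo S, 1/S | Azacitidine S, 1/S |
|---|---|---|---|
| Cycle 7 | 5.52 | 0.809, 1.24 | 0.862, 1.16 |
| Cycle 13 | 11.04 | 0.654, 1.53 | 0.743, 1.35 |
| Cycle 25 | 22.08 | 0.427, 2.34 | 0.551, 1.81 |

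Treatment discontinuation adds to this. With an assumed median time on treatment of 6 to 12 months, the Cycle 13 factor is 3.58 to 1.89. Cycles 1-2 are not diluted at entry.

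**The case against.** The strongest reply is that fatal infections are well reported. They have their own overall and by-cycle tables, and death makes an event serious, so the serious tables hold them beside non-fatal cases. The AESI EAIR has no grade limit. The maximum-severity table lets a reader add Grades 3, 4 and 5 for each preferred term. All of this stands, and it rules out the reading that fatal infections are lost from the report or that every severe-event display omits them. It does not supply a Grade 3 to 5 EAIR or by-cycle table.

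Three further limits stand. Exposure stops at death, so an early fatal case adds little person-time; the fault is the missing numerator. The Grade 5 line in Protocol 11.2.2 belongs to the fallback scale for events not defined in CTCAE; that fatal CTCAE-listed infections are also graded 5 is an assumption here. And a subject with a separate Grade 3 or 4 infection record may remain in the row, at least at system organ class or AESI level.

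On denominators, the whole-group rule comes from a general default and not from a sentence in SAP 11.1.1. SAP 9.2 also tabulates number of cycles, so the numbers reaching later cycles may be largely recoverable. Both points are fair, but a default that nothing overrides is what a programmer would follow.

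A reader might also infer that constant risk would be shown as steadily falling. The documents do not support that, because the cycle groups span 2, 2, 2, 6 and 12 cycles and then an open end. A constant per-cycle risk giving 20% over two cycles gives 1 − 0.8³ = 48.8% over six and 1 − 0.8⁶ = 73.8% over twelve. With an assumed 60% and 30% reaching Cycles 7 and 13, and no attrition within groups, the tables would show 29% and 22%. The distortion is real, but it is not a simple decline.

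**Conclusion.** Both parts hold as gaps in the planned safety displays. The grade-limited tables and the severe EAIR omit subjects whose only record of an event is fatal, and no EAIR or by-cycle output puts Grades 3 to 5 together. The 5% to 34% shortfall is illustrative, since the documents give no counts. A reader might infer from Protocol 1.4.1 that the cut favors azacitidine. That would follow if fatal-only infections made up a larger share of severe cases on that arm, which the documents suggest but do not quantify.

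Later-cycle percentages are understated under the protocol's default denominator: by factors of about 1.5 (placebo) and 1.35 (azacitidine) at the start of Cycle 13, from planned mortality alone. These figures rest on exponential survival at the planning medians and no discontinuation, so larger factors are likely in practice. How unequal the arms become depends on actual attrition.

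No confirmatory test or stated figure changes. The point merits action because it alters safety comparisons in a trial whose named signal is early death with infection as leading cause.

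**What to change.** 1. In SAP 11.1, 11.1.1 and 11.1.2, add incidence tables, by-cycle tables and an EAIR for Grade 3 or higher (3 to 5), with each subject counted once. Keep the Grade 3 or 4 and fatal rows. State how the greatest-severity rule applies in the grade-limited tables.
2. In SAP 11.1.1, set the denominator for each cycle group to the subjects in that arm who were dosed in the first cycle of the group, and print that N in the column header. Because the groups differ in width, also give a rate per person-time within each group wherever risk is to be compared over time.

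The cost is wording, programming and a few more tables. Direct comparability with studies that report only Grade 3 or 4 is slightly reduced, and keeping that row limits the loss. SAP 11 already permits extra safety analyses. Since Protocol Amendment 6.0 records the primary study report as final, these would be supplementary outputs. Appendix J sends Extension Phase adverse events to Protocol 10.7, which has the same cut, so the Grade 3 or higher row should be added there too.

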11.1.1. Adverse Events by Cycle

The following TEAEs will be summarized by incidence tables, for the safety population by treatment group and cycle group:

- All TEAEs
- Serious TEAEs
- TEAEs with severity of grade 3 or 4;
- TEAEs leading to death
- Treatment-related TEAE leading to death
- TEAEs leading to study medication discontinuation

The following cycle group will be used:

- Cycles 1-2

- Cycles 3-4
- Cycles 5-6
- Cycles 7-12
- Cycles 13-24
- Cycles > 24

The analysis of TEAE by cycle of onset for any occurrence will be based on the onset date of AE to determine the cycle. AEs with a duration that overlaps multiple cycles will only be counted in the first overlapped cycle. Subjects with multiple occurrences reported with the onset date within the same cycle for the same SOC / PT will be counted once per SOC level / PT level within the cycle.

TEAEs by cycle day of onset for any occurrence will also be summarized. The cycle day will be grouped as: cycle days 1-7, cycle days 8-14, cycle days 15-21, and cycle days >21.

The first occurrence of TEAEs by cycle of onset, and by cycle day of onset will be summarized by SOC and PT. Subjects with multiple occurrences reported for the same SOC / PT will be counted only once based on the earliest onset date (the first occurrence) per SOC level / PT level.

11.1.2. Adverse Events of Special Interest

The AEs described in this section have been identified as treatment-emergent AEs of special interest (AESI) based on the known safety profile of azacitidine. These treatment-emergent AESI include those adverse events which Celgene is actively monitoring.

AESIs refer to a group of terms/PTs from one or more SOCs relating to a defined medical condition or area of interest. The AESI category or term refers to the group of PTs, rather than the individual PT. Standardized MedDRA queries (SMQs) or company MedDRA queries based on specific SOC, higher level terms (HLT) or PTs were used to define the categories of AEs of special interest.

TEAEs will be summarized for the following categories of AESIs, by PT and treatment group:

- Myelosuppression,
 - Neutropenia
 - Thrombocytopenia
 - Anemia
 - General myelosuppression
- Hemorrhagic events
- Infection
- Hepatic failure
- Renal failure
- Ischemic colitis

- Gastrointestinal events
- Interstitial lung disease
- Tumour lysis syndrome
- Cardiac events:
 - Cardiac arrhythmias
 - Myocardial infarction
 - Cardiac failure
- Anxiety, Confusional State, Insomnia
- Psychiatric Disorders

Separate frequency tables will be provided for the AESIs identified above by AESI category, PT and treatment group:

- Summary of AESIs;
- All AESIs;
- Treatment-related AESIs;
- Serious AESIs;
- Treatment-related serious AESIs;
- AESIs with severity of grade 3 or 4;
- AESIs leading to death;
- AESIs leading to death by cycle of onset;
- Treatment-related AESIs leading to death;
- AESIs leading to dose reduction;
- AESI leading to dose interruption;
- AESI leading to dose interruption and dose reduction;
- AESIs leading to study medication discontinuation;
- Treatment-related AESI leading to study drug discontinuation;
- AESI with EAIR.

The summaries of all AESIs, serious AESIs, AESIs with severity of grade 3 or 4, AESIs leading to death, and AESIs leading to study medication discontinuation will also be presented by cycle group as defined in Section 11.1.1.

Additional safety analyses may be displayed by specific parameters, (e.g. time to occurrence, demographics, exposure/duration) if warranted. Similarly, other selected listings may be necessary to assist with analysis of the safety data.

